3.1. Study Treatment

All patients will receive bosutinib at a starting dose of 400 mg QD. The dose of bosutinib may be escalated (up to a maximum of 600 mg QD) for unsatisfactory response or reduced (down to 300 mg QD, and further to a minimum of 200 mg QD only when approved by the sponsor) for toxicity.

Each patient will receive daily bosutinib for up to approximately 3 years after registration of the last patient (12 months [48 weeks] Core Treatment Phase and the following ≥ 24 months [96 weeks] Extension Phase) or until the end of the study, treatment failure, unacceptable toxicity, death, or withdrawal of consent occurs.

Details of the study treatment forms and packaging, and recommendations for dose modifications are included in the Study Treatments Section 5 of the protocol.

4. PATIENT ELIGIBILITY CRITERIA

This study can fulfill its objectives only if appropriate patients are enrolled. The following eligibility criteria are designed to select patients for whom participation in the study is considered appropriate. All relevant medical and nonmedical conditions should be taken into consideration when deciding whether a particular patient is suitable for this protocol.

Patient eligibility should be reviewed and documented by an appropriate member of the investigator's study team before patients are included in the study.

4.1. Inclusion Criteria

Patients must meet all of the following inclusion criteria to be eligible for enrollment into the study:

1. Diagnosis of CP CML of ≤ 6 months (from initial diagnosis)
 - Diagnosis of CP CML with molecular confirmation by detection of BCR-ABL rearrangement at screening (cytogenetic assessment for Ph is not required for enrollment; however, patients with known Ph- CML prior to registration are not eligible for this study); diagnosis of CP CML will be defined as all of the following per European LeukemiaNet (ELN) definitions:

- a. <15% blasts in peripheral blood and bone marrow;
 - b. <30% blasts plus promyelocytes in peripheral blood and bone marrow;
 - c. <20% basophils in peripheral blood;
 - d. $\geq 100 \times 10^9/L$ platelets ($\geq 100,000/mm^3$);
 - e. No evidence of extramedullary disease except hepatosplenomegaly; AND
 - f. No prior diagnosis of AP or BP-CML.
2. Age ≥ 20 years.
 3. Eastern Cooperative Oncology Group (ECOG) performance status (PS) 0 or 1.
 4. Adequate Renal Function, including:
 - a. Serum creatinine $\leq 1.5 \times$ upper limit of normal (ULN) or estimated creatinine clearance ≥ 60 mL/min as calculated using the method standard for the institution.
 5. Adequate Liver Function, including:
 - a. Total serum bilirubin $\leq 1.5 \times$ ULN unless the patient has documented Gilbert syndrome;
 - b. AST and ALT $\leq 2.5 \times$ ULN; $\leq 5.0 \times$ ULN if there is liver involvement by leukemia;
 6. Able to take oral tablets.
 7. Resolved acute effects of any prior therapy to baseline severity or CTCAE Grade ≤ 1 except for AEs not constituting a safety risk by investigator judgment.
 8. Serum pregnancy test (for females of childbearing potential) negative at screening.

Female patients of nonchildbearing potential must meet at least 1 of the following criteria:

- a. Achieved postmenopausal status, defined as follows: cessation of regular menses for at least 12 consecutive months with no alternative pathological or physiological cause; status may be confirmed with a serum follicle-stimulating hormone (FSH) level confirming the postmenopausal state;
- b. Have undergone a documented hysterectomy and/or bilateral oophorectomy;
- c. Have medically confirmed ovarian failure.

All other female patients (including female patients with tubal ligations) are considered to be of childbearing potential.

9. Evidence of a personally signed and dated informed consent document indicating that the patient has been informed of all pertinent aspects of the study.
10. Willing and able to comply with scheduled visits, treatment plan, laboratory tests, and other study procedures.

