5.4.2. Dosing Interruptions and Dose Reductions

The dose of bosutinib may be interrupted and/or reduced for the toxicities described below.

For bosutinib, a dose reduction from 400 mg QD to 300 mg QD is permitted. If a patient requires a second dose reduction from 300 mg QD to 200 mg QD, the investigator should contact the sponsor to determine if the patient may continue on treatment at a lower dose. The second dose reduction must be approved by the sponsor and will only be considered if the patient in question displays optimal response to bosutinib treatment at the time point at which the dose reduction is being considered. Patients should remain on the 200 mg dose for a maximum of 4 weeks or until the toxicity resolves, whichever is sooner, in line with the dose reduction and dose escalation guidelines. The dose may then be re-escalated following the escalation guidelines. Any patient on the 200 mg dose with ongoing toxicity after the 4-week time point will be discontinued from treatment and will continue with Long-Term Follow-Up evaluations. Dose reductions of bosutinib below 200 mg QD will not be permitted.

If the investigator and the sponsor decide that it is not in the best interest of the patient to remain on treatment at a dose lower than 300 mg QD, the patient will be discontinued from treatment and will continue with Long-Term Follow-Up evaluations.

Once the dose has been reduced for a patient, patients should remain on that dose unless the toxicity resolves (Grade ≤ 1). In that case, the dose may be escalated to the previous starting dose.

Management of Non-Hematologic Treatment-Related Toxicities

The management of non-hematologic treatment-related toxicities is summarized in [Table 2](#).

Patient instructions for the management of diarrhea are presented in [Appendix 6](#).

Table 2. Management of Non-Hematologic Treatment-Related Toxicity

Adverse Event	Action
Elevated liver transaminases	If elevations in ALT, AST >5× institutional ULN occur, bosutinib should be interrupted until recovery to ≤ 2.5×ULN and may be resumed at 400 mg QD thereafter. If recovery takes longer than 4 weeks, discontinuation of bosutinib should be considered. If transaminase elevations ≥3×ULN occur concurrently with bilirubin elevations >2×ULN and alkaline phosphatase <2×ULN, bosutinib should be discontinued.
Diarrhea	For Grade 3/4 diarrhea, bosutinib should be interrupted and may be resumed at 400 mg QD upon recovery to Grade ≤ 1.
Grade 1	Current dose level.

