 - Preexisting AST or ALT baseline values above the normal range: AST or ALT values >2 times the baseline values AND $>3 \times$ ULN; or $>8 \times$ ULN (whichever is smaller).

- Preexisting values of TBili above the normal range: TBili level increased from baseline value by an amount of at least $1 \times \text{ULN}$ **or** if the value reaches $>3 \times \text{ULN}$ (whichever is smaller).

Rises in AST/ALT and TBili separated by more than a few weeks should be assessed individually based on clinical judgment; any case where uncertainty remains as to whether it represents a potential Hy's Law case should be reviewed with the sponsor.

The patient should return to the investigator site and be evaluated as soon as possible, preferably within 48 hours from awareness of the abnormal results. This evaluation should include laboratory tests, detailed history, and physical assessment. The possibility of hepatic neoplasia (primary or secondary) should be considered.

In addition to repeating measurements of AST and ALT and TBili, laboratory tests should include albumin, creatine kinase (CK), direct and indirect bilirubin, gamma-glutamyl transferase (GGT), prothrombin time (PT)/international normalized ratio (INR), total bile acids, alkaline phosphatase and acetaminophen drug and/or protein adduct levels. Consideration should also be given to drawing a separate tube of clotted blood and an anticoagulated tube of blood for further testing, as needed, for further contemporaneous analyses at the time of the recognized initial abnormalities to determine etiology. A detailed history, including relevant information, such as review of ethanol, acetaminophen (either by itself or as a coformulated product in prescription or over-the-counter medications), recreational drug, supplement (herbal) use and consumption, family history, sexual history, travel history, history of contact with a jaundiced person, surgery, blood transfusion, history of liver or allergic disease, and potential occupational exposure to chemicals, should be collected. Further testing for acute hepatitis A, B, C, D, and E infection and liver imaging (eg, biliary tract) may be warranted.

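### Table 2's fixed liver limits do not fit the raised baseline liver tests admitted by two exceptions in Protocol 4.1 item 5

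*Protocol*

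**What the plan says.** **Entry (Protocol 4.1, item 5).** AST and ALT may be up to 2.5×ULN, or up to 5.0× "ULN if there is liver involvement by leukemia". Total bilirubin may be up to 1.5×ULN "unless the patient has documented Gilbert syndrome", and in that case no upper limit is given. Item 1e permits hepatosplenomegaly, so enlargement of the liver does not rule a patient out.

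**Hold and restart (Protocol 5.4.2, Table 2, liver row).** If ALT or AST exceeds 5× the institutional ULN, "bosutinib should be interrupted until recovery to" 2.5×ULN or lower. If that takes more than 4 weeks, discontinuation is to be considered.

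**Discontinuation (same row).** The drug is to be stopped if transaminases of at least 3×ULN "occur concurrently with bilirubin elevations" above 2×ULN with alkaline phosphatase below 2×ULN. Neither the row nor the table's footnotes mention the patient's baseline. The table is headed "Table 2. Management of Non-Hematologic Treatment-Related Toxicity".

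**Text that leans on the row.** After Table 2, Section 5.4.2 bars dose escalation in patients whose transaminases are elevated as the table describes. Section 6.5 lets investigator and sponsor agree to continue a patient whose hold exceeds 4 weeks or who needs less than 300 mg.

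**Liver-injury reporting (Protocol 8.4.2).** Separate thresholds are set for "Preexisting AST or ALT baseline values above the normal range", and likewise for bilirubin that is raised at baseline.

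**The concern.** The entry criteria knowingly admit two kinds of patient whose liver tests are abnormal for reasons other than bosutinib. The dosing rules for the same tests are then written as if every patient had started near normal. A patient with leukemic liver involvement who is held must fall to a level that was not required at entry, while off the drug that treats the leukemia. A patient with Gilbert syndrome can meet a discontinuation rule largely on a bilirubin value that was present at screening.

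Three things are at stake. A patient may be kept off drug, or taken off it, because of baseline and not toxicity. A patient who stops treatment before Week 48 moves to telephone follow-up and will usually have no Week 48 central PCR. SAP 5.3.1.1 counts that as non-response unless MMR is shown at both Week 36 and Week 60. The same patient also enters a single-arm safety profile as a hepatic discontinuation.

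**Working it through.** The plan states no figure on this point, so there is none to reproduce. The check sets the limits against each other, in multiples of ULN.

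**Inputs.** B = entry ALT or AST: at most 2.5, or at most 5.0 with liver involvement (4.1 item 5). T = entry bilirubin: at most 1.5, uncapped in Gilbert syndrome (4.1 item 5). Hold above 5; restart at 2.5 or below; stop at ALT/AST ≥3 with bilirubin >2 and alkaline phosphatase <2 (Table 2). The 8.4.2 rules for raised baselines are used for comparison only. The values of B and T below are illustrative.

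**Formulas.**
- Fold rise from entry to the hold limit = 5.0 / B
- Restart limit as a share of entry = 2.5 / B
- 8.4.2 transaminase threshold = min(max(2B, 3), 8)
- 8.4.2 bilirubin threshold for raised T = min(T + 1, 3)

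**Step 1: transaminases alone.**

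| Entry ALT (B) | Fold rise to hold | Restart limit / entry | ≥3 limb met at entry? | 8.4.2 threshold |
|---|---|---|---|---|
| 2.5 (general limit) | 2.00 | 100% | no | >5.0 |
| 3.0 | 1.67 | 83% | yes | >6.0 |
| 4.0 | 1.25 | 62.5% | yes | >8.0 |
| 4.5 | 1.11 | 56% | yes | >8.0 |
| 5.0 (exception limit) | 1.00 | 50% | yes | >8.0 |

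For any B above 2.5, the restart limit is below the patient's own entry value. At B = 4.9, a rise to 5.1 is 5.1/4.9 − 1 = 4.1% and triggers a hold. Restart then needs a value 1 − 2.5/4.9 = 49.0% below entry.

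**Step 2: Gilbert syndrome alone.** Take T = 2.2, B = 2.4 and alkaline phosphatase <2, which is eligible. The bilirubin limb (>2) is met at baseline. ALT rising to 3.0 (3.0/2.4 − 1 = 25%) with unchanged bilirubin meets the discontinuation rule. For comparison, 8.4.2 would need ALT above 2 × 2.4 = 4.8 and bilirubin above min(3.2, 3) = 3.

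**Step 3: both exceptions.** Take B = 4.0, T = 2.5 and alkaline phosphatase <2, which meets item 5. All three components of the Table 2 stopping rule are present before the first dose. The 8.4.2 thresholds would be >8 for ALT and min(3.5, 3) = 3 for bilirubin.

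**Step 4: everyone else.** With B ≤ 2.5, ALT must at least double to reach the hold limit, and the restart limit is not below entry. With T ≤ 1.5, the bilirubin limb is not met at entry. No eligible patient exceeds the hold limit at entry, since ≤5.0 and >5 only touch.

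**Step 5: weight in the primary endpoint.** One patient in 60 is 1/60 = 1.7 percentage points of the MMR rate.

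**The case against.** A reader might infer that the entry, dosing and Hy's Law rules give one patient irreconcilable instructions. The documents do not support that. Table 2 governs dosing; 8.4.2 governs work-up and SAE reporting. A site can stop the drug under Table 2 in a patient who is not a potential Hy's Law case and comply with both texts. What 8.4.2 does show is that raised baselines were foreseen. Nor is Table 2 unclear about its reference: it says ULN throughout, and fixed limits are a legitimate cautious choice.

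Three provisions soften the effect. The title of Table 2 restricts it to treatment-related toxicity, and stable Gilbert bilirubin or leukemic ALT is arguably not that. Exclusion 13 lets the investigator keep out a patient whose laboratory abnormality raises the risk of participation. After 4 weeks, stopping is only to be considered, and 6.5 allows continuation by agreement. A hold alone does not make a patient a non-responder.

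Most of this stands, but it does not close the gap. The liver row gives no way to separate drug effect from a raised baseline. The discretion in 6.5 covers long holds and doses below 300 mg, not the combined transaminase and bilirubin rule. Table 3, by contrast, is expressly limited to patients with normal or higher counts, or in CHR. The plan thus ties hematologic dose rules to the patient's hematologic state, while the liver row has no counterpart.

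**Conclusion.** The point holds for patients admitted under the two exceptions in 4.1 item 5, and only for them. For entry ALT/AST above 2.5×ULN, the restart limit is below the entry value, by up to half. For Gilbert syndrome with bilirubin above 2×ULN and alkaline phosphatase below 2×ULN, only the transaminase limb remains to be met. With both exceptions, the stopping values can precede treatment.

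This rests on a literal reading of Table 2, in which a value driven partly by baseline counts as an elevation, and on alkaline phosphatase below 2×ULN for the stopping rule. The documents give no expected number of such patients. The ALT rates they quote (31% any grade in BFORE; 23% Grade 3/4 in BELA, at 500 mg) describe whole trial populations, so they cannot be read as the frequency of this problem.

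A reader might also infer that the primary analysis is compromised. It is not: the hypothesis test, sample size and power are unaffected, and each patient lost this way would lower the observed MMR rate by at most 1.7 points. Low priority, but more than missing detail, because following the rules as written can keep a patient off drug, or direct discontinuation, on baseline values.

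**What to change.** Reconcile four places for patients admitted with raised baseline liver tests: 4.1 item 5, the liver row of Table 2, the paragraph after Table 2 that uses the row to bar dose escalation, and the discretion in 6.5. State how the hold, restart and discontinuation limits apply to a patient admitted under either exception. The test of the revised text is that no patient eligible under 4.1 meets a stopping rule before the first dose, or faces a restart limit below the entry value, unless the protocol says that this is intended. Section 8.4.2 needs no change on this account. Which limits apply is for the sponsor's medical team.

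The cost is one footnote to Table 2 and a matching sentence in 6.5. Because dosing rules are touched, it may need an amendment and not just an administrative letter. No extra data, visits or patients are required, and the SAP is unchanged.

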4.2. Exclusion Criteria

Patients with any of the following characteristics/conditions will not be included in the study:

1. Any prior medical treatment for CML, including TKIs, with the exception of hydroxyurea treatment, which is permitted for up to 6 months prior to registration.
2. Any past or current CNS involvement, including leptomeningeal leukemia.
3. Extramedullary disease only.
4. Major surgery or radiotherapy within 14 days prior to registration.
5. History of clinically significant or uncontrolled cardiac disease including:
 - History of, or active, congestive heart failure;
 - Uncontrolled angina or hypertension within 3 months prior to registration;
 - Myocardial infarction within 12 months prior to registration;
 - Clinically significant ventricular arrhythmia (such as ventricular tachycardia, ventricular fibrillation, or Torsades de pointes);
 - Diagnosed or suspected congenital or acquired prolonged QT interval history or prolonged QTc (QTcF should not exceed 500 msec);
 - Unexplained syncope.
6. Patients with active, uncontrolled bacterial, fungal, or viral infection, including hepatitis B virus (HBV), hepatitis C virus (HCV), known human immunodeficiency virus (HIV) or acquired immunodeficiency syndrome (AIDS)-related illness.
7. Recent or ongoing clinically significant GI disorder (eg, Crohn's disease, ulcerative colitis, or prior total or partial gastrectomy).
8. History of another malignancy within 5 years prior to registration with the exception of basal cell carcinoma or cervical carcinoma in situ or Stage 1 or 2 cancer that is

considered adequately treated and currently in complete remission for at least 12 months.

9. Uncontrolled hypomagnesemia or uncorrected hypokalemia due to potential effects on the QT interval.
10. Known prior or suspected severe hypersensitivity to study drugs or any component in their formulations.
11. Investigator site staff members directly involved in the conduct of the study and their family members, site staff members otherwise supervised by the investigator, or patients who are Pfizer employees, including their family members, directly involved in the conduct of the study.
12. Participation in other studies involving investigational drug(s) within 30 days or 5 half-lives of investigational product, whichever is longer, prior to registration and/or during study participation.
13. Other acute or chronic medical or psychiatric condition including recent (within the past year) or active suicidal ideation or behavior or laboratory abnormality that may increase the risk associated with study participation or investigational product administration or may interfere with the interpretation of study results and, in the judgment of the investigator, would make the patient inappropriate for entry into this study.
14. Pregnant female patients; breastfeeding female patients; fertile male and female patients of childbearing potential who are unwilling or unable to use 2 highly effective methods of contraception as outlined in this protocol for the duration of the study and for at least 28 days after the last dose of investigational product.

4.3. Lifestyle Requirements

In this study, fertile male patients and female patients who are of childbearing potential as applicable to the study will receive bosutinib, which has been associated with suspected teratogenicity/fetotoxicity. Patients who are, in the opinion of the investigator, sexually active and at risk for pregnancy with their partner(s) must agree to use 2 methods of highly effective contraception throughout the study and for at least 28 days after the last dose of bosutinib. The investigator or his or her designee, in consultation with the patient, will confirm that the patient has selected 2 appropriate methods of contraception for the individual patient and his/her partner(s) from the list of permitted contraception methods (see below) and will confirm that the patient has been instructed in their consistent and correct use. At time points indicated in the schedule of activities table, the investigator or designee will inform the patient of the need to use 2 highly effective methods of contraception consistently and correctly and document the conversation, and the patient's affirmation, in the patient's chart. In addition, the investigator or designee will instruct the patient to call immediately if 1 or both of the selected contraception methods is discontinued or if pregnancy is known or suspected in the patient or partner.

Highly effective methods of contraception are those that, alone or in combination, result in a failure rate of less than 1% per year when used consistently and correctly (ie, perfect use) and include the following:

1. Established use of hormonal methods of contraception associated with inhibition of ovulation (eg, oral, inserted, injected, implanted, transdermal), provided the patient or male patient's female partner plans to remain on the same treatment throughout the entire study and has been using that hormonal contraceptive for an adequate period of time to ensure effectiveness.
2. Correctly placed copper-containing intrauterine device (IUD).
3. Male condom or female condom used WITH a separate spermicide product (ie, foam, gel, film, cream, or suppository). For countries where spermicide is not available or condom plus spermicide is not accepted as highly effective contraception, this option is not appropriate.
4. Male sterilization with absence of sperm in the postvasectomy ejaculate.
5. Bilateral tubal ligation/bilateral salpingectomy or bilateral tubal occlusive procedure (provided that occlusion has been confirmed in accordance with the device's label).

All sexually active male patients must agree to prevent potential transfer to and exposure of partner(s) to drug through ejaculate by using a condom consistently and correctly, beginning with the first dose of investigational product and continuing for at least 28 days after the last dose of investigational product.

4.4. Sponsor's Qualified Medical Personnel

The contact information for the sponsor's appropriately qualified medical personnel for the study is documented in the study contact list located in the study organization.

To facilitate access to an appropriately qualified medical personnel on study-related medical questions or problems, patients are provided with a contact card. The contact card contains, at a minimum, protocol and investigational product identifiers, patient study numbers, contact information for the investigator site, and contact details for a contact center in the event that the investigator site staff cannot be reached to provide advice on a medical question or problem originating from another healthcare professional not involved in the patient's participation in the study. The contact number can also be used by investigator staff if they are seeking advice on medical questions or problems; however, it should be used only in the event that the established communication pathways between the investigator site and the study team are not available. It is therefore intended to augment, but not replace, the established communication pathways between the investigator site and the study team for advice on medical questions or problems that may arise during the study. The contact number is not intended for use by the patient directly, and if a patient calls that number, he or she will be directed back to the investigator site.

